UTI is the most common serious bacterial infection in children. It confers a significant health burden on society, affecting approximately 2.6-7.5% of febrile children and resulting in more than 1.1 million physician visits each year. UTI can be divided into an infection of the lower tract (bladder) or upper tract (kidney). A kidney infection- also known as pyelonephritis- represents a severe illness associated with systemic symptoms and signs such as fever, rigors and costovertebral angle tenderness. Pyelonephritis may occur because the kidney is seeded from a blood borne source or, more commonly, from an infection that has ascended from the bladder. Short term complications of pyelonephritis include sepsis and acute renal failure. The treatment for pyelonephritis can usually be undertaken on an outpatient basis, but occasionally the severity of illness requires a hospital admission. In the United States, about 4.7% of children diagnosed in the emergency room with UTI will be admitted to the hospital. The hospital admission rate for pyelonephritis has not decreased and is possibly increasing. 4

Scarring: a sequelae of pyelonephritis.

Irreversible renal scarring may be a consequence of pyelonephritis and an independent risk factor for chronic kidney disease.5 After the acute inflammatory process resolves, histopathology of an area of scar will show chronic tubulointerstitial inflammation and fibrosis6. Nuclear imaging will show a defect of the renal contour which represents focal loss of renal tissue. Not every episode of pyelonephritis will lead to scarring, but one episode of pyelonephritis is sufficient to result in scarring.7 About 15% to 52% of individuals will exhibit renal scarring following pyelonephritis.8-10 Renal scarring in an individual with vesicoureteral reflux- a urinary tract defect in which an abnormal uretero-vesical junction promotes the

PI: [name]

retrograde flow of urine from the bladder to the kidneys- can lead to reflux nephropathy. Reflux nephropathy is the third leading cause of chronic renal insufficiency and the fourth leading cause of end stage renal disease (ESRD) among children in North America.11 Significant renal scarring may also lead to hypertension in 17% to 30% of children which in turn may enhance the progression of renal insufficiency and failure.8

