When pyelonephritis is induced in animal models, DMSA scans are highly sensitive and reliable for detecting and localizing the acute parenchymal inflammation using histopathology as the gold standard.6 Areas of infection will correspond to areas within the kidney of reduced uptake of DMSA with preservation of the renal outlines. Scars within the kidney are represented by areas of decreased uptake of DMSA with loss of renal contour or cortical thinning.6, 9, 18 In practice, the DMSA is a routine test to look for scarring and when the clinical picture is not clear, to diagnose acute pyelonephritis. The unattractive aspect to performing a DMSA scan is the requirement of intravenous access for injection of the radiotracer, radiation exposure (mean effective dose 2.84 mSv; a CT scan is 2-5 mSv as a reference), and an exam time of 2-3 hours.19 For these reasons, the DMSA scan is performed judiciously. In cases of suspected pyelonephritis, the approach of empiric antibiotic treatment based on the clinical picture is much more common than performing a DMSA scan to confirm diagnosis. In cases where the clinical picture of pyelonephritis is coherent (when symptoms and lab data correlate), it is common practice to initiate empiric antibiotic treatment without the use of imaging to confirm diagnosis. However, there remain many complex situations when the diagnosis of pyelonephritis is not clear and symptoms or lab results will be atypical or unreliable. The DMSA scan remains useful to confirm diagnosis pyelonephritis in these patients. If Quick MRI proves to be an accurate imaging modality for pyelonephritis, it could substitute for a DMSA scan in these cases.

Quick MRI

MRI is an imaging method that can provide both excellent morphological detail and functional information regarding the urinary tract without the necessity for ionizing radiation. These features make MRI an attractive and useful modality for pediatric practice. However, enthusiasm for its use is tempered by high cost and its sensitivity to movement artifact that can significantly impair image resolution. Young children, therefore, need to be sedated during the long scanning time of conventional MRI. The potential adverse effects of sedation include the exposure to a general anesthetic and possibility of hypoxemia, paradoxical reactions, and an inadequate study.

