- 1) To establish the feasibility of completing the quick renal MRI compared to the DMSA scan (using DMSA as the 'gold standard') among children with suspected urinary tract infections (UTI). Children admitted to the American Family Children's Hospital for suspected acute pyelonephritis will undergo a clinical DMSA renal scan and quick renal MRI.
- 2) To establish the sensitivity and specificity of the quick renal MRI compared to the DMSA scan (using DMSA as the 'gold standard') in the diagnosis of renal scars among children with recurrent UTI. Children with recurrent UTI will undergo a clinical DMSA renal scan and quick renal MRI. The sensitivity and specificity of the quick renal MRI to detect renal scars will be determined using DMSA as the standard.

RESEARCH DESIGN AND METHODS

Design and Methods

If study criteria are met for Aim 1, patients will be enrolled during their hospital stay and undergo both a quick renal MRI and a standard of care DMSA scan before discharge. During the patients hospital stay, they will be offered the chance to participate. The PI, a hospital, and/or [name] will be available to recruit and onboard patients. If the patient chooses to do so, they will be consented, and the DMSA and Quick MRI will be schedule to occur within one week of consent, either before or after they are discharged.

If the criteria are met for Aim 2, a DMSA scan will be recommended according to the CDC's Spina Bifida Registry protocol. Patients are also allowed to participate in Aim 2 if they've completed a DMSA scan within the past 6 months. Patients will also be invited to participate in the study by undergoing a quick renal MRI. Spina bifida patients will be identified as qualified for the study ahead of time by the research staff, and will be asked if they would like to participate at their next regularly scheduled clinic visit. If they do choose to participate, they will then be scheduled to receive the DMSA and Quick MRI within 6 months.

For aim 1 patients, there is no specific order for the scans, but both imaging tests should be performed within one week of each other. For Aim 2, there is no specific order for the scans, but they should be performed within six months of each other.

Neither group of patients would experience a delay in receiving antibiotics because it is standard of care.

Patient enrollment and the success of participants completing both studies will be evaluated every 2 months.

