If the recruitment rate is less than 50% of that planned to be completed by 6 months into the study, we will be prepared to expand recruitment to pediatric patients at St. Mary's Hospital.

To enroll additional patients likely to have renal scarring we will contact families of children with spina bifida who have already had a DMSA performed in the past year and invite them to participate. We believe that the quick, non-invasive nature of the test and the accommodated scheduling will appeal to potential subjects. The hospitalist faculty staff are enthusiastic for the development of the quick MRI and are likely to be early adopters of the quick renal MRI; this will facilitate enrollment for Aim 1.

Likewise, for Aim 2, [name] understands that many of her patients are engaged in spina bifida advocacy and will be motivated to participate in a study that promises to ease their lifelong burden of frequent invasive testing.

Quick MRI Imaging: MRI of the kidneys will be performed using a 1.5-Tesla magnet (Signa, GE Medical Systems Milwaukee, Wisconsin, USA). For pyelonephritis, axial diffusion weighted imaging sequences will be used (3 mins if respiratory triggered, 15 secs if patient can hold breath). For renal scar, coronal and axial T1-weighted fat-saturated sequences will be used (10 mins). Below are the specific sequences of the Quick MRI abdomen without contrast for all study patients. Particular sequences were selected based on prior case reports of their accuracy in diagnosing either pyelonephritis or renal scars. All 5 sequences will be done because it will be important to distinguish acute infection from scarring, as well as renal anatomy.

Sequence	Pyelonephritis	Renal scars					
Coronal and axial T1 FAT		Х					
Axial T1 FAT		Х					
Axial DWI	X						
Coronal T2 SSFSE	Gives detail of re	Gives detail of renal collecting system					
Coronal T1 LAVA-Flex	Gives detail of re	Gives detail of renal vasculature					

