A quick MRI scan takes about 15 mins or less. No IV or sedation will be necessary. The patient will be required to lie flat and still during the test. A parent will be allowed to be with the patient while they are in the scanner. The machine will produce loud intermittent sounds of banging or knocking so they will have to wear protective headphones. They can listen to music if you want. If they are less than 1 year old, they will be swaddled and can be "held" during the test. If a child needs to have a parent in the scanner, it is ideal if the parent can have their head near the patients' legs and arms stretched out to hold the childs' hands. If the parent needs to be by the patients' head, it can be accomplished by the parent lying head to head with the child or the parent lying on the child. Ideally they are lying head to head, or just outside of the scanner reaching in.

Subject Population

Inclusion Criteria

Our target population is a heterogeneous group of medically complex patients with atypical UTIs. Our pilot study will help to establish the feasibility of the Quick MRI protocol in these patients.

For Aim 1: All children ages 0-21 years admitted to AFCH for a febrile UTI, suspected pyelonephritis, or diagnosed pyelonephritis will be eligible. Those who undergo DMSA scan as clinically indicated will be approached for study participation.

We want to establish the sensitivity of Quick MRI in the diagnosis of pyelonephritis and as such, we have selected a group of patients with febrile UTI who have a high probability of having pyelonephritis. We have determined that patients admitted to the hospital for intravenous hydration and antibiotics fulfill this criterion. This approach includes patients who would normally receive DMSA scans, therefore, a separate trip to the hospital will be unnecessary in patients that complete the imaging tests prior to discharge. These would be potential deterrents to successful recruiting from an outpatient basis. However, due to the nature of our study and recruiting conditions, we will also allow patients to return after their inpatient stay in order to complete the imaging result, whichever may work better for the patient and family.

For Aim 2: All children ages 0-21 years seen in the AFCH Spina Bifida Multi-Disciplinary Clinic for routine-follow-up will be eligible. Patients will be screened for a history of more than 1 UTI in the past year.

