All patients must be willing to undergo the Quck MRI and, depending on which aim, the DMSA scan in order to be included.

Exclusion Criteria

For Aim 1: Patients will be excluded from the study of patients with acute pyelonephritis if they do not have evidence of pyuria on their UA, if their urine culture is negative, or are not comfortable having a quick MRI completed.

For both Aims: Patients with contraindications to MRI will be excluded from eligibility (implanted devices such as pacemakers, implanted cardioverter defibrillators, or cochlear implants or if they are or are planning to become pregnant).

Data Collection, Handling, Storage

Subjects' confidentiality will be addressed in multiple ways. There will be a retrospective and prospective review of the data. Data from eligible patients' medical records will be entered into an Excel document. All study records will be kept in secure locations. All data will be maintained only on Department of Urology password- and firewall-protected computers, and on the Department of Orthopedics/Rehabilitation and Urology;s secured network server. Data will not be stored on laptops, notebooks, or other portable computers. The PI has a locked office in a security restricted building (Medical Foundation Centennial Building). Only team members will have access to the data. Data about study subjects will not be shared with anyone other than team members.

The study team will do the following things to ensure the privacy of research participants and confidentiality of data:

- use codes so that no direct subject identifiers are recorded on data collection sheets
- create codes for data that are not based on subject identifiers (i.e., avoid codes that include subject initials or are based on birth dates)
- store the links to the code and code separately from each other
- keep identifiable data in locked cabinets or drawers in rooms with restricted access and/or on password-protected computers housed in rooms with restricted access or housed on departmental servers with limited, password-protected access
- limit the number of participating site team members with access to directly identifiable information

After imaging scans are performed, only DMSA scans will be accessible to the providers via Healthlink. Data/images will be analyzed by [name], and [name] and appropriate radiology staff. Results of data analysis will be passed to research coordinator in order to document findings.

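### Aim 2 scores a scar formed between two scans up to six months apart as a quick MRI error, and the plan neither records nor analyses UTIs in that gap

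*Combined protocol and SAP*

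**What the plan says.** **Timing.** Design and Methods sets the Aim 2 interval: "For Aim 2, there is no specific order for the scans, but they should be performed within six months of each other". It also accepts an existing scan: "Patients are also allowed to participate in Aim 2 if they've completed a DMSA scan within the past 6 months". Later in the same section, an additional recruitment route invites families of children with spina bifida "who have already had a DMSA performed in the past year". For Aim 1, by contrast, "both imaging tests should be performed within one week of each other".

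**Population.** Under Inclusion Criteria for Aim 2: "Patients will be screened for a history of more than 1 UTI in the past year". No minimum time since the last UTI is given. Under Exclusion Criteria, only one rule reaches Aim 2: "For both Aims: Patients with contraindications to MRI will be excluded from eligibility".

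**Disease process.** Background and Significance states: "About 15% to 52% of individuals will exhibit renal scarring following pyelonephritis". It adds that a single episode can be enough. Under Current imaging standard it describes acute infection on DMSA: "Areas of infection will correspond to areas within the kidney of reduced uptake of DMSA". There the renal outline is preserved, whereas a scar shows contour loss or cortical thinning.

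**Analysis.** DMSA is the gold standard. Statistical Considerations defines sensitivity as TP over TP plus FN and specificity as TN over TN plus FP, with no rule for pairs in which a UTI occurred between the scans.

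**The concern.** The two-by-two table assumes that both scans see the same kidney. Aim 1 protects that assumption with a one-week window. Aim 2 allows up to six months, in children chosen because they have had repeated UTIs.

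If a scar forms in the gap, the later scan can show it and the earlier one cannot. With MRI first, the pair becomes a false negative. With DMSA first, it becomes a false positive. Neither is a fault of the MRI.

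Aim 2 is judged against a hypothesis of at least 80% sensitivity and specificity (end of the Quick MRI background), and the sensitivity estimate rests on about 19 scarred children. If the result falls short and UTI dates were not kept, nobody can tell a poor test from elapsed time.

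**Working it through.** **1. The plan's own sample size.** Inputs from Statistical Considerations: power at least 80%, significance 0.05, prevalence 30%, sensitivity 60% against 90%, specificity 70% against 90%. Sidedness is not stated. A one-sample exact binomial test with 0.025 in the upper tail gives:
- Sensitivity: 19 scarred children (reject at 16 or more; tail 0.023, power 0.885). 19/0.30 = 63.3, so 64.
- Specificity: 31 unscarred children (power 0.807). 31/0.70 = 44.3, so 45.

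The larger is 64, as stated. At 64, the expected split is 19.2 scarred and 44.8 unscarred.

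**2. Chance of a new scar, r.**
- From the plan: 15% to 52% scarring after pyelonephritis.
- Assumed: UTIs continue at 2 per year as a Poisson process, 25% of them are pyelonephritis (range 10–50%), and true sensitivity and specificity are both 90%.

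Formula: r = [1 − exp(−2 × share × gap in years)] × scarring risk.
- Three months: 1 − exp(−0.125) = 0.1175, so r = 0.018 to 0.061.
- Six months: 1 − exp(−0.25) = 0.221, so r = 0.033 to 0.115.

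**3. Apparent accuracy when all pairs share one order.**
- MRI first: sensitivity = (0.9 × 19.2 + 0.1 × 44.8r) / (19.2 + 44.8r).
- DMSA first: specificity = 0.9(1 − r) + 0.1r.

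**4. Apparent accuracy when half the pairs are in each order.**
- Sensitivity: as in step 3, with r/2 in place of r.
- Specificity = [(0.9 − 0.8r) + 0.9(1 − r)] / (2 − r).

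| Scenario (25% share) | Sensitivity | Specificity |
|---|---|---|
| 3-month gap, mixed order | 88–85% | 89–87% |
| 6-month gap, all MRI first | 84–73% | 90% (unchanged) |
| 6-month gap, all DMSA first | 90% (unchanged) | 87–81% |

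Over the full 10–50% share range, the mixed three-month case runs from 89% to 81% sensitivity and from 90% to 85% specificity. At six months in one order, the range is 87% to 64% sensitivity or 89% to 74% specificity.

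**5. Weight of one pair.** With 19 scarred children, one child is 1/19 = 5.3 points. If the misattributed child joins the DMSA-positive group as an extra false negative, sensitivity goes from 17.28/19.2 = 90% to 17.28/20.2 = 85.5%. Either way, one pair moves it by about 5 points. This does not depend on the assumed UTI rate.

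**6. Cost of excluding affected pairs.** At 2 UTIs a year, the chance of no UTI at all is exp(−1) = 0.37 over six months and exp(−0.5) = 0.61 over three.
- Six months: 64 × 0.37 ≈ 24 pairs, about 7 scarred. Even 7 of 7 cannot reject 60%, since 0.6^7 = 0.028 exceeds 0.025.
- Three months: about 39 pairs, about 12 scarred, power 0.66.

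**The case against.** The strongest reply is that the size rests on stacked assumptions. More than one UTI in the past year is a selection criterion, not a continuing rate, and children picked on a recent high count may have fewer later. The background separates bladder from kidney infection and ties scarring to the latter, and the documents give no pyelonephritis share. The 15–52% describes individuals who show scarring after pyelonephritis, not the risk of a new scar in a scar-free child. Six months is the maximum gap. The order is free, and accepting a prior DMSA favours DMSA first, which spares sensitivity. All of this stands as a limit on the size. None of it removes the mechanism.

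A reader might also infer that acute DMSA defects will routinely be counted as scars. The documents do not support that. The background distinguishes the two by contour, and every patient gets diffusion-weighted imaging because infection must be told apart from scarring. What remains is narrower: the contour distinction is background text rather than an Aim 2 reading rule, and the diffusion sequence informs the MRI read, not the DMSA reference. Neither addresses a scar formed between scans.

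Finally, this is a pilot whose stated threshold for losing enthusiasm is 60%. Even the most extreme case in the working (64% sensitivity, 74% specificity) stays above it in expectation. The 80% hypothesis is the more exposed benchmark.

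**Conclusion.** The point holds as a gap in data capture and analysis. Followed as written, the plan charges real scarring between scans to the MRI, and nothing in the documents corrects this.

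The moderate scenario is a loss of about 2 to 5 points in sensitivity and 1 to 3 in specificity. The 84–73% sensitivity and 87–81% specificity figures are upper scenarios and should not be read as the expected result. They need every pair at six months in a single order, and they share the assumed UTI rate and pyelonephritis share. With about 19 scarred children, though, one or two such pairs could decide whether the 80% hypothesis appears to be met.

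Two further inferences are not supported. The sample size of 64 is not wrong on its own inputs; it reproduces exactly. Nor does the concern justify making UTI-free pairs the main estimate: that could leave about 7 scarred children, and it would move the estimate away from the recurrent-UTI population that Aim 2 names.

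**What to change.** 1. In the medical-record review already described under Data Collection, Handling, Storage, record both scan dates, the scan order, and the dates of febrile or culture-proven UTI shortly before the DMSA and between the scans.
2. Keep all pairs as the main Aim 2 estimate. Pre-specify a sensitivity analysis that excludes pairs with a febrile or culture-proven UTI between scans, and show results by scan order and by interval.
3. State the background's own description (loss of renal contour or cortical thinning) as the rule for reading a DMSA as scar-positive in Aim 2.
4. Reconcile the past-year DMSA route with the six-month limit. The two passages conflict, and the longer route would widen the gap in DMSA-first pairs.

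**Cost.** A little more chart abstraction and one additional analysis, with no scan moved. The documents confirm record review but not that UTI dates will be complete, so missing dates should be reported. The sensitivity analysis will be imprecise because few scarred children will remain in it, and it should be read as a check on direction. This is a cheap improvement.

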We will include our initial study evaluation (at 25% of targeted enrollment) in the soonest following continuing review. In the case that our evaluation shows negative results and occurs prior to a continuing review, we will contact the IRB with the information and seek to reevaluate or possible discontinue the study. All study team members have completed relevant training materials, are well versed in maintaining clinical integrity and data validity, and will be formally instructed in the proper application of this protocol. Data/images will be evaluated by the PI, [name], and [name], a study team member. This data will be passed to the research coordinator, whereupon it will be stored securely as outlined in the Data and Record Keeping section of our protocol. The primary data handlers, [name] and the research coordinator, meet every two weeks and can discuss and evaluate protocol adherence, data integrity, and validity as needed during these meetings.

STATISTICAL CONSIDERATIONS

Aim 1 will determine the sensitivity of quick MRI in the diagnosis of suspected acute pyelonephritis in children with febrile UTI. With a power of at least 80%, a target significance level of 0.05, and an estimate of 90% prevalence of DMSA confirmed acute pyelonephritis among children admitted for febrile UTI, the minimum sample size required to detect a change in sensitivity from 80%-90% is 34 subjects.

Aim 2 will determine the sensitivity and specificity of quick MRI in the diagnosis of renal scars in children with spina bifida and recurrent UTIs. With a power of at least 80%, a target significance level of 0.05, and an estimate of 30% prevalence of DMSA confirmed renal scars in this patient group, the minimum sample size required to detect a change in sensitivity from 60-90% and a change in specificity from 70-90% would require a minimum sample size of 64 subjects.

The sensitivity will be calculated with TP/TP+FN. The specificity will be calculated with TN/TN+FP

This is a pilot study and we are trying to get a baseline understanding of the accuracy of Quick MRI. If the preliminary sensitivity/specificity percentages are less than 60%, we would be less enthusiastic about carrying out future research on this question, and vice versa.

REFERENCES

- 1. Freedman, A. L.: Urologic diseases in North America Project: trends in resource utilization for urinary tract infections in children. J Urol, **173**: 949, 2005

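### The Aim 1 sample size uses an unsourced 90% prevalence for all febrile UTI admissions, but recruitment is limited to children with a clinically indicated DMSA, for whom the protocol gives no prevalence

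*Combined protocol and SAP*

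**What the plan says.** Statistical Considerations sizes Aim 1 on three inputs: "With a power of at least 80%, a target significance level of 0.05", then "an estimate of 90% prevalence of DMSA confirmed acute pyelonephritis among children admitted for febrile UTI", giving the result that "the minimum sample size required to detect a change in sensitivity from 80%-90% is 34 subjects". No source is cited for the 90%. The same section defines sensitivity as TP/(TP+FN).

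The Aim 1 inclusion criteria start from the population that the 90% describes: "All children ages 0-21 years admitted to AFCH for a febrile UTI, suspected pyelonephritis, or diagnosed pyelonephritis will be eligible". The next sentence narrows it: "Those who undergo DMSA scan as clinically indicated will be approached for study participation". The same section describes the target population as "a heterogeneous group of medically complex patients with atypical UTIs".

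Current imaging standard, in the background, explains who has this scan. When symptoms and laboratory data agree, children are commonly treated without imaging; the scan is used "when the clinical picture is not clear, to diagnose acute pyelonephritis".

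Design and Methods describes the sequence differently. Families are offered participation during the stay and, if they accept, "they will be consented, and the DMSA and Quick MRI will be schedule to occur within one week of consent".

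**The concern.** The prevalence is quoted for one group and recruitment draws on another. On the protocol's own account, the children whose pyelonephritis is clearest are those who usually go unscanned, so a DMSA-selected group could contain a smaller share of positives than all admissions.

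This matters because DMSA-negative children contribute nothing to sensitivity. The Aim 1 target is counted in children enrolled, so the number who inform the estimate is 34 times the prevalence. If the prevalence is lower than assumed, the precision and power of the sensitivity result fall with it. The plan reports power at one prevalence only, so a reader cannot see how much depends on that figure.

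**Working it through.** **Inputs.** From Statistical Considerations: sensitivity 80% versus 90%, power at least 80%, significance level 0.05, prevalence 90%, N = 34. The test and its sidedness are not stated. The prevalence among children with a clinically indicated DMSA is not in the documents, so I assume a range of 50% to 90%.

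**1. The plan's own figure.** For a one-sample test of a proportion in DMSA-positive children:

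n = [(z₁₋α/₂ √(p₀q₀) + z₀.₈₀ √(p₁q₁)) / (p₁ − p₀)]²

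= [(1.960 × 0.4 + 0.842 × 0.3) / 0.10]² ≈ 107.4, rounded up to 108 positives.

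N = 108 / 0.90 = 120.

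Other forms also miss 34: one-sided normal 93, exact two-sided 119, exact one-sided 92, and the smallest (one-sided, variance under the alternative only) 63. The figure 34 is close to what 70% versus 90% would need (exact two-sided, 31 positives; 31 / 0.90 = 34.4), but the plan does not state that contrast for Aim 1.

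**2. Expected positives, precision and power at N = 34.** Expected positives are 34 × prevalence. Intervals are Clopper-Pearson for an observed sensitivity as near 90% as whole numbers allow. Power is for 80% versus 90% by exact binomial test, averaged over the number of positives distributed as Binomial(34, prevalence).

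| Assumed prevalence | Expected positives | Example | Exact 95% CI | Power, two-sided | Power, one-sided |
|---|---|---|---|---|---|
| 90% | 30.6 | 28/31 | 74-98% | 18% | 34% |
| 80% | 27.2 | 24/27 | 71-98% | 18% | 27% |
| 70% | 23.8 | 22/24 | 73-99% | 13% | 25% |
| 60% | 20.4 | 18/20 | 68-99% | 11% | 20% |
| 50% | 17.0 | 15/17 | 64-99% | 8% | 16% |

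The observed proportions differ slightly from row to row (28/31 is 90.3%, 22/24 is 91.7%, 15/17 is 88.2%), so the intervals show the trend and are not a strict like-for-like comparison. Two-sided power is the same at 90% and 80% because the exact test moves in steps.

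**3. Hand check of one point.** With exactly 31 positives, the two-sided test rejects 80% only at 30 or 31 detected. At a true sensitivity of 90% that has probability 31 × 0.9³⁰ × 0.1 + 0.9³¹ = 0.131 + 0.038 = 0.17. With 16 or fewer positives it can never reject, since 0.8¹⁶ = 0.028 exceeds 0.025.

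**4. Prevalence matters for any N.** The 108 positives from step 1 would need 108 / 0.90 = 120 children, 108 / 0.70 = 155, or 108 / 0.50 = 216.

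**The case against.** The strongest reply is that the protocol gives reasons to expect high positivity. The inclusion criteria say the group was chosen for its high probability of pyelonephritis, on the ground that these children are admitted for intravenous fluids and antibiotics. Children with diagnosed pyelonephritis are eligible too. The exclusion criteria remove children without pyuria or with a negative culture, and so remove part of the unclear group. This stands as a limit on the point: the size of any drop is unknown. It does not supply a prevalence, because the argument rests on admission and not on selection for DMSA, and none of these criteria is linked to the 90%.

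A second reply is that the sections on recruitment can be read together: a DMSA is clinically indicated, the family is approached, and both scans are then scheduled. That reading is possible. The text does not settle it, and a reading in which any eligible admission may be approached would fit the 90% better.

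A third is that this is a pilot, with Aim 1 framed as feasibility and a 60% benchmark for further interest. Even 15/17 has a lower limit of 64%, above that benchmark. This lowers the stakes, but the plan still makes a power claim.

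A reader might also infer more than the documents support:

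- **That 90% is wrong and far fewer positives will follow.** No figure for the recruited group exists, so neither can be shown.
- **That a shortfall would go unseen.** The positive count is the denominator of TP/(TP+FN) and will appear when sensitivity is calculated.
- **That prevalence alone takes power from 73% to 35%.** Those figures, at 90% and 50% prevalence, are for 70% versus 90%, a contrast not stated for Aim 1.

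**Conclusion.** The point holds as an unsupported assumption. The 90% carries no source, is quoted for all febrile UTI admissions, and is applied to a DMSA-selected subgroup that the protocol elsewhere describes as unclear or atypical.

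Over an assumed 50% to 90%, informative children range from 17 to about 31, and the lower confidence limit for an observed sensitivity near 90% moves from about 74% to 64%. For the stated contrast, exact two-sided power falls from about 18% to 8%.

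Prevalence is the smaller of two problems. The claim of at least 80% power already fails at the plan's own 90%, where about 120 children would be needed by the two-sided normal formula. Correcting the prevalence would not repair that; a lower prevalence makes it worse. The figures assume a one-sample exact test at 0.05 and that every enrolled child has both scans readable.

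**What to change.** - Keep 34. State which group the prevalence describes, make it the group actually approached, and give a source or label it an assumption.
- Replace the single power statement with a short table of expected DMSA-positive children, exact interval width and power for 80% versus 90%, over 50% to 90% prevalence. The table under the working can serve.
- Reconcile Design and Methods with the Aim 1 inclusion criteria on which children are approached relative to the DMSA order. This review takes no position on when that scan should be ordered.

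Two apparent remedies should be avoided. A target of 31 DMSA-positive children would endorse a number with about 17% power for the stated contrast, and could mean enrolling more children to reach it. Acting on positivity at the 25% evaluation would rest on 34 × 0.25 = 8.5 children: 8/9 positive has an exact 95% interval of 52-100% and 6/9 one of 30-93%, which hardly separates 90% from 60%.

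The cost is protocol wording and one table, with no new procedure or enrolment. The downside is that the stated precision and power will look less favourable.
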